3.3 Inclusion of Women and Minorities

Both men and women of all races and ethnic groups are eligible for this trial.

4. REGISTRATION PROCEDURES

4.1 General Guidelines for DF/HCC Institutions

Institutions will register eligible participants in the Clinical Trials Management System (CTMS) OnCore. Registrations must occur prior to the initiation of protocol therapy. Any participant not registered to the protocol before protocol therapy begins will be considered ineligible and registration will be denied.

An investigator will confirm eligibility criteria and a member of the study team will complete the protocol-specific eligibility checklist.

Following registration, participants may begin protocol therapy. Issues that would cause treatment delays should be discussed with the Overall Principal Investigator (PI). If a participant does not receive protocol therapy following registration, the participant's registration on the study must be canceled. Registration cancellations must be made in OnCore as soon as possible.

4.2 Registration Process for DF/HCC Institutions

DF/HCC Standard Operating Procedure for Human Subject Research Titled *Subject Protocol Registration* (SOP #: REGIST-101) must be followed.

5. TREATMENT PLAN

5.1 Treatment Regimen

Prexasertib (LY2606368) will be administered on day 1 and day 15 of a 28 day cycle. Prexasertib will be given at the recommended phase II dose of 105 mg/m². Treatment will be administered on an outpatient basis. Reported adverse events and potential risks are described in **Section 7**. Appropriate dose modifications are described in **Section 6**. No other investigational or commercial agents or therapies may be administered with the intent to treat the participant's malignancy, with the exception of palliative radiation therapy to non-target lesions which may be administered with the principal investigator's agreement. Maintenance hormonal therapy for breast or prostate cancer patients will be permitted as long as the therapy was started prior to the initiation of the study medication. Bisphosphonate use is permitted.

5.2 Pre-Treatment Criteria

5.2.1 Cycle 1, Day 1 Infusion

Patients who completed screening assessments > 72 hours prior to cycle 1 day 1 should

have cycle 1 day 1 laboratory values that re-meet eligibility criteria. If screening assessments were completed ≤ 72 hours prior to cycle 1 day 1, laboratory tests do not need to be repeated on cycle 1 day 1 and the screening laboratory values can be used as the cycle 1 day 1 values.

5.2.2 Subsequent Infusions

Please refer to **Section 6** for toxicity management guidelines.

5.3 Agent Administration

5.3.1 Administration Instructions

Prexasertib (LY2606368) will be given at the recommended phase II dose of 105 mg/m² and should be administered IV over 1 hour (+/- 5 minute infusion window) using a central or free flowing peripheral IV line with an in-line, sterile, non-pyrogenic, 0.22- μ m filter. Prexasertib should not come in contact with normal saline or Lactated Ringer's solution; the infusion line should be flushed with 5% dextrose injection (D5W) before and after prexasertib administration. The infusion should be completed within 4 hours of priming the infusion set.

Prexasertib should be handled according to standard procedures and precautions consistent with a cytotoxic anticancer drug.

Body surface area (BSA) should be calculated per institutional standards. Dose recalculation for changes in participant weight should be made in accordance with institutional standards.

5.3.2 Hypersensitivity Reactions

Prexasertib mesylate monohydrate is formulated in Captisol® (sulfobutylether- β -cyclodextrin [SBECD]), which has been associated with allergic reactions. The etiology of the hypersensitivity reactions observed with prexasertib mesylate monohydrate is not known.

The patient should be monitored for signs and symptoms indicative of an infusion-related reaction for the duration of the infusion (including nausea, dizziness, chest pain, diaphoresis, flushing, decreased blood pressure, shortness of breath, hypoxia, and tachycardia). In the event of a suspected infusion reaction, institutional guidelines for managing infusion reactions should be followed. For subsequent infusions, premedication with diphenhydramine hydrochloride (dosing per investigator discretion) and/or other premedication as per institutional standards or investigator discretion may be administered. The infusion rate may also be decreased by 50 percent.

5.3.3 Serotonin Syndrome

In non-clinical assessments, prexasertib interacts with multiple 5-hydroxytryptamine (5-HT) receptors. Patients should be monitored for symptoms of serotonin syndrome, including autonomic changes (tachycardia, mydriasis, diaphoresis, or body temperature increases), mental status changes (restlessness or anxiety), and neurological hyperexcitability (tremor, hyperreflexia, or myoclonus).

If observed, appropriate treatment (e.g., cyproheptadine or octreotide) may be used as a treatment. As of 13 January 2017, serotonin syndrome had not been reported for any patient receiving prexasertib.

5.4 General Concomitant Medication and Supportive Care Guidelines

Investigators should use appropriate supportive medications to address toxicities that arise during the study, including but not limited to antiemetics, antidiarrheals, and blood product transfusion.

5.4.1 Antibiotic and Granulocyte Colony Stimulating Factor Administration

Prophylactic antibiotics should be considered for use in patients that have experienced febrile neutropenia or patients deemed at higher risk for febrile neutropenia by the treating investigator.

Prophylactic Granulocyte Colony Stimulating Factor (G-CSF) such as filgrastim (or equivalent), as well as pegfilgrastim (or equivalent), are permitted in accordance with the American Society of Clinical Oncology (ASCO) guidelines. Primary or secondary prophylactic G-CSF support is permitted.

5.4.2 Medications Known or Suspected to cause Prolonged QTc Intervals or Torsades de Pointes

On days when prexasertib (LY2606368) is administered, patients should avoid taking multiple concomitant medications that are known or suspected to cause prolonged QTc or Torsades de Pointes (see **Appendix B**). If possible, alternative agents should be considered.

5.4.3 Other Anticancer Therapy

No other investigational or commercial agents or therapies may be administered with the intent to treat the participant's malignancy, with the exception of palliative radiation therapy to non-target lesions which may be administered with the principal investigator's agreement. Bisphosphonates are permitted. Maintenance hormonal therapy for breast or prostate cancer patients will be permitted as long as the therapy was started prior to the initiation of the study medication. Consideration of other medications for pre-existing conditions may be approved on a case-by-case basis by the overall principal investigator.

5.4.4 Other Concomitant Medication Guidelines

The potential risk of a clinical DDI with either CYP1A2 or CYP2D6 substrates is minimal. Therefore, there are no recommended restrictions on CYP1A2 or CYP2D6 substrates.

5.5 Criteria for Taking a Participant Off Protocol Therapy

Duration of therapy will depend on individual response, evidence of disease progression, and tolerance. In the absence of treatment delays due to adverse event(s), treatment may continue indefinitely or until one of the following criteria applies:

- Disease progression (unless the participant is exhibiting clinical benefit as agreed upon with the principal investigator)
- Intercurrent illness that prevents further administration of treatment
- Unacceptable adverse event(s)
- Pregnancy
- Participant demonstrates an inability or unwillingness to comply with the trial regimen
- Participant decides to withdraw from the protocol therapy
- General or specific changes in the participant's condition render the participant unacceptable for further treatment in the judgment of the treating investigator

Participants will be removed from the protocol therapy when any of these criteria apply. The reason for removal from protocol therapy, and the date the participant was removed, must be documented in the case report form (CRF). Alternative care options will be discussed with the participant.

The research team will update the relevant Off Treatment information in OnCore.

In the event of unusual or life-threatening complications, treating investigators must immediately notify the Overall PI, [name], PhD at [contact].

5.6 Duration of Follow Up

Participants will be followed for serious adverse events (SAEs) for 30 days after removal from protocol therapy or until death, whichever occurs first. Participants will be followed for survival status only until death after removal from protocol therapy. Survival follow up will be performed

by review of the medical record, contact with care providers, and/or telephone contact as needed every 3 to 4 months.

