1.3 Secondary Objectives

- 1) To assess toxicity following CHK1 inhibition among participants in these cohorts.
- 2) To examine the objective response and overall survival rate following CHK1 inhibition in these patient cohorts.

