6.2 Specific Toxicity Management

6.2.1 Hematologic Toxicity Management

6.2.1.1 Neutropenia

Neutropenia has been the most frequent and severe toxicity following treatment with prexasertib (LY2606368) every 14 days, with grade 3 or greater decreases in neutrophil count deemed related to prexasertib treatment having been observed in approximately three-quarters of patients. In general, neutrophil counts nadir on day 8 and grade 4 decreases are often transient (e.g., less than 5 days). Febrile neutropenia has been reported in approximately 11% of patients, but no patients have died due to febrile neutropenia. Please refer to **Section 5.4.1** for G-CSF guidelines.

Table 5: Management of Neutropenia	
Toxicity	Prexasertib Dose Management
Uncomplicated Grade 3 Neutropenia (ANC < 1 K/uL)	Hold infusion until recovery to grade 2, resume at same dose level.
Grade 3 Neutropenia Associated with a Fever or Infection (ANC < 1 K/uL)	Hold infusion until recovery to grade 2, resume with one dose level reduction.
Uncomplicated Grade 4 Neutropenia < 7 Consecutive Days in Duration (ANC < 0.5 K/uL)	Hold infusion until recovery to grade 2, resume at same dose level.
Grade 4 Neutropenia ≥ 7 Consecutive Days in Duration (ANC < 0.5 K/uL)	Hold infusion until recovery to grade 2, resume with one dose level reduction.

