7.2 Serious Adverse Events

A serious adverse event (SAE) is any adverse event that occurs after the initial dose of study treatment, during treatment, or within 30 days of the last dose of treatment that results in one of the following outcomes:

- Death
- Hospitalization for greater than 24 hours
- Prolonging an existing inpatient hospitalization
- A life-threatening experience (that is, immediate risk of dying)
- Persistent or significant disability/incapacity
- Congenital anomaly/birth defect
- Considered significant by the investigator for any other reason

Previously planned (prior to signing the informed consent form) surgeries, and non-disease related elective surgeries planned during the course of the study, should not be reported as SAEs unless the underlying medical condition has worsened or appeared during the course of the study. Events that occur prior to the first administration of study medication should not be reported as SAEs.

Preplanned hospitalizations or procedures for preexisting conditions that are already recorded in the patient's medical history at the time of study enrollment should not be considered SAEs. Hospitalization or prolongation of hospitalization without a precipitating clinical AE (e.g., for the administration of study therapy or other protocol-required procedure) should not be considered SAEs.

Important medical events that may not result in death, be life-threatening, or require hospitalization may be considered SAEs when, based on appropriate medical judgment, they

may jeopardize the patient and may require medical or surgical intervention to prevent one of the outcomes listed in this definition.

Death due to disease progression should not be reported as an SAE unless the investigator deems it to be related to the use of study drug.

Study site personnel must alert Eli Lilly of any SAE as soon as possible and no later than 24 hours of the investigator and/or institution receiving notification of the SAE experienced by a patient participating in the study. The SAE reports should be on a standard reporting form (e.g. CIOMS, MedWatch 3500a, or similar) and are to be sent to Eli Lilly via fax at [name].

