7.6 Routine Adverse Event Reporting

[figure not shown]
All Adverse Events **must** be reported in routine study data submissions to the Overall PI on the toxicity case report forms. **AEs reported through expedited processes (e.g., reported to the IRB, FDA, etc.) must also be reported in routine study data submissions.**

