10. STUDY CALENDAR

Baseline evaluations are to be conducted within 14 days prior to start of protocol therapy, with the exception of the informed consent and baseline tumor imaging which may be obtained up to 28 days prior to the start of protocol therapy. Assessments must be performed prior to

administration of any study agent.

	Table 10: Study Calendar								
	Screening ^a	Cycle 1 Day 1	Cycle 1 Day 8 ^b	Cycle 1 Day 15 ⁱ	Cycle 1 Day 22 ^h	Cycle 2+ Day 1 ⁱ	Cycle 2+ Day 15 ⁱ	Off Treatment ^k	Every 3 Months After Discontinuing ^l
Prexasertib (LY2606368)^b		X		X		X	X		
Informed consent	X								
Demographics	X								
Medical history	X								
Physical exam	X	X	X	X	X	X	X	X	
Vital signs^c	X	X	X	X	X	X	X	X	
Height	X								
Weight	X	X		X		X	X	X	
ECOG performance status	X	X		X		X	X	X	
CBC w/diff & Plt	X	X	X	X	X	X	X	X	
Serum chemistry^d	X	X	X	X	X	X	X	X	
β-HCG^e	X							X	
EKG^f	X	X				X			
Adverse Events		X	X	X	X	X	X	X	
Radiologic evaluation	X	CT or MRI imaging of any disease-involved site. Radiologic measurements should be performed at the end of cycle 2 (cycle 2 day 28) and at the end of every 2 cycles of treatment thereafter (i.e. cycle 4 day 28, cycle 6 day 28, and so on). There is a ± 7 day window on imaging evaluations.						X	
Fresh Tumor Biopsy^g	X								
Research Germline Blood Sample for	X								

Table 10: Study Calendar									
	Screening ^a	Cycle 1 Day 1	Cycle 1 Day 8 ^b	Cycle 1 Day 15 ⁱ	Cycle 1 Day 22 ^h	Cycle 2+ Day 1 ^j	Cycle 2+ Day 15 ⁱ	Off Treatment ^k	Every 3 Months After Discontinuing ^l
WES^g									
Research Blood Samples for cfDNA		X	cfDNA samples to be collected at the visit immediately following a restaging scan (i.e., cycle 3 day 1, cycle 5 day 1, cycle 7 day 1, and so on) as described in Section 9 .					X	
Telephone or Care Provider Contact									X

a) Screening evaluations are to be performed within 14 days of cycle 1 day 1, with the exception of the informed consent and baseline tumor imaging which may be obtained up to 28 days prior to cycle 1 day 1.
 b) Prexasertib (LY2606368) dose as assigned; see administration guidelines in **Section 5**.
 c) Heart rate, respiratory rate, blood pressure, temperature, and oxygen saturation (O₂ sat). On infusion days, vital signs are to be collected anytime pre-infusion (exact time of vital signs should be recorded). May be repeated as clinically indicated.

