 d) Sodium, potassium, chloride, CO₂, blood urea nitrogen (BUN), creatinine, glucose, albumin, total protein, alkaline phosphatase, total bilirubin, SGOT [AST], SGPT [ALT], globulin, and magnesium. Other tests may be ordered as clinically indicated.
 e) Serum pregnancy test only required for women of childbearing potential. Childbearing potential defined as any female who has experienced menarche and who has not undergone successful surgical sterilization (hysterectomy, bilateral tubal ligation or bilateral oophorectomy) or is not postmenopausal (defined as amenorrhea >12 consecutive months; or women with a documented plasma follicle-stimulating hormone level >35μIU/mL).
 f) To be performed at screening, at any time pre-dose on cycle 1 day 1, upon completion of the first infusion (+15 minute window from the end of the infusion), and 1 hour after the end of the infusion (+30 minute window). EKG to be completed pre-dose (any time prior to the infusion) on the first day of each subsequent cycle. Additional EKGs may be performed as clinically indicated at the treating investigator's discretion. If QTcF increases > 30 msec from screening EKG at any time point, EKG should be repeated at 10 minutes after the end of the infusion (± 5 minute window), 30 minutes after the end of the infusion (± 10 minute window), and 1 hour after the end of the infusion (+30 minute window). The exact time of all EKGs should be recorded.
 g) Baseline fresh tumor biopsy and germline blood sample for WES required for the patients enrolled during Stage 1 of the HR and replicative stress cohorts. Please see **Section 9** for further detail.
 h) Cycle 1 day 8 and cycle 1 day 22 may be shifted by ± 3 days for scheduling issues (vacations, holidays, adverse weather, etc.).
 i) Day 15 assessments and infusion may shifted ± 1 day for scheduling issues (vacations, holidays, adverse weather, etc.).
 j) The start of a subsequent cycle may be delayed by up to 7 days for scheduling issues (vacations, holidays, adverse weather, etc.).
 k) Off-treatment evaluation. Note: follow up visits or other contact is required in order to identify SAEs during the 30 days following the end of study treatment.
 l) Participants will be followed until death or withdrawal of consent after removal from protocol therapy for survival status only. This follow up will be performed by review of the medical record, contact with care providers, and/or telephone contact as needed every 3 to 4 months.

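### Non-serious adverse events are collected only up to an Off Treatment evaluation with no stated timing, so late toxicity of the last infusion may be missed and toxicity rates may be biased low.

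*Combined protocol and SAP*

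**What the plan says.** Section 5.6 sets the rule after treatment ends: "Participants will be followed for serious adverse events (SAEs) for 30 days after removal from protocol therapy", or until death if sooner, with survival status as the only other item followed. Footnote k of Table 10 (section 10) repeats the restriction: "follow up visits or other contact is required in order to identify SAEs during the 30 days following the end of study treatment".

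Table 10 also has an Adverse Events row that is not limited to serious events. It is marked at each cycle 1 visit (days 1, 8, 15 and 22), at days 1 and 15 of later cycles, and at Off Treatment. The only column after that, for contact every 3 months, has no adverse event mark. Footnote k gives the Off Treatment evaluation no day or window.

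Section 7.6 requires all adverse events to "be reported in routine study data submissions to the Overall PI on the toxicity case report forms", but sets no period over which they are to be sought. Section 7.2 starts the serious event clock differently from 5.6, counting events "during treatment, or within 30 days of the last dose of treatment that results in one of the following outcomes".

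Toxicity is a secondary objective (1.3): "To assess toxicity following CHK1 inhibition among participants in these cohorts". Section 13.3 analyses it in all who received drug, including those who did not complete a cycle. Section 13.5.1 says toxicity evaluation begins at first treatment; no section says when it ends.

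**The concern.** For every participant, collection of non-serious events closes at a visit whose distance from the last infusion is not fixed. Most of what the plan expects would be non-serious. Section 2.1.2.5 describes non-hematologic toxicity as mainly grade 1 or 2, with fatigue and nausea the most frequent related events. Contact that asks only about serious events would not be expected to pick these up.

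At stake is the accuracy of the per-patient toxicity rates. Missing events can only lower them. Participants who stop early have few or no earlier infusions over which an event could already have been recorded, and 13.3 deliberately keeps them in the analysis. The primary endpoint, progression-free status at 4 months, is not affected.

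**Working it through.** The plan states no toxicity rate, precision target or threshold, so there is no figure of its own to reproduce. The check has two parts: whether the calendar allows an early Off Treatment evaluation, and what that could cost.

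**Timing**

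Inputs: infusions on days 1 and 15 of 28-day cycles (5.1); first restaging at cycle 2 day 28, ± 7 days (Table 10); and, as the one toxicity whose timing is given, "neutrophil counts nadir on day 8" (6.2.1.1), which is about 7 days after an infusion.

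- Cycle 2 day 15 is study day 28 + 15 = 43. Cycle 2 day 28 is day 56, so the scan may fall on days 49 to 63.
- If day 43 is the last infusion, the scan comes 49 − 43 = 6 to 63 − 43 = 20 days later, nominally 13. An Off Treatment evaluation at or after the scan usually falls at or beyond the day-8 point.
- Cycle 3 day 1 is day 57, still inside the scan window. A participant may be infused on day 57, scanned by day 63, found to have progressed, and evaluated off treatment before day 57 + 7 = 64.
- Stops for unacceptable toxicity, withdrawal or intercurrent illness (5.5) are not tied to a scan and can lead to an evaluation at any interval after an infusion.

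So an early evaluation is possible under the plan as written, though not the usual course after a scheduled scan.

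**Size, as an illustration**

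Inputs: related fatigue in P = 25.8% and nausea in P = 11.7% of patients at the study dose and interval (2.1.2.5). Assumptions, not in the documents: equal and independent risk q at each of k infusions, and a fraction f of last-infusion events missed.

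- Risk per infusion: q = 1 − (1 − P)^(1/k)
- Loss from the per-patient rate: f × q × (1 − q)^(k−1), because only a participant with no earlier event can be misclassified.

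Fatigue with k = 4: q = 1 − 0.742^(1/4) = 0.0719; (1 − q)^3 = 0.7995; product 0.05747. If everything after the last infusion were missed (f = 1), the loss would be 5.7 points, and the observed rate 20.1%.

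Loss in percentage points:

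| Event | k | q | f = 0.1 | f = 0.25 | f = 0.5 | f = 1 |
|---|---|---|---|---|---|---|
| Fatigue | 1 | 25.8% | 2.6 | 6.5 | 12.9 | 25.8 |
| Fatigue | 2 | 13.9% | 1.2 | 3.0 | 6.0 | 11.9 |
| Fatigue | 4 | 7.2% | 0.6 | 1.4 | 2.9 | 5.7 |
| Nausea | 4 | 3.1% | 0.3 | 0.7 | 1.4 | 2.8 |

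The rows for k = 1 and 2 hold P at 25.8% with fewer infusions, which raises the assumed risk per infusion. They show how the loss concentrates in early stoppers and do not predict the rate in the whole cohort.

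Grade 4 neutropenia is not used as an illustration. After cycle 1, Table 10 schedules blood counts only on days 1 and 15, so a short day-8 nadir has no scheduled count even during treatment. A follow-up contact would not add one.

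**The case against.** The strongest reply is that the plan does collect non-serious events after the last infusion. The Table 10 row "Adverse Events X X X X X X X" has its seventh mark at Off Treatment, alongside physical examination, vital signs, blood count and chemistry. Section 7.6 sends all adverse events to the case report form. After a scheduled scan, that evaluation will usually fall at or after the day-8 point, and the day-57 example needs several things to coincide. Events that matter clinically can still be captured: the serious event definition in 7.2 includes anything the investigator considers significant, and 5.5 requires the reason for removal to be documented. Toxicity carries no decision rule, and recording only serious events after a final visit is a legitimate design choice.

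Much of this stands. A reader might infer from 5.6 alone that non-serious toxicity of the last infusion is lost as a rule, or that the rates are certainly biased low. The Off Treatment mark rules out the first reading, and nothing in the documents establishes the second. The independence assumption may also overstate the loss: if some patients are more susceptible, more first events fall in earlier infusions, where they are recorded.

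The reply does not cover events that begin after an early Off Treatment evaluation. Section 7.6 says what to do with an event once known but schedules no enquiry, and footnote k limits the enquiry that is scheduled to serious events.

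**Conclusion.** The concern holds in a limited form. Non-serious events are sought up to and including an Off Treatment evaluation with no stated timing; after it, the plan calls only for serious event and survival follow-up. When that evaluation comes soon after the last infusion, later non-serious symptomatic events have no scheduled collection, and toxicity rates may be understated, mainly in participants who stop after one or two infusions.

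The size cannot be determined, because the documents give neither the interval to the evaluation nor the onset times of fatigue and nausea. For fatigue at k = 4, the range for f between 0.1 and 0.5 is a plausible illustration; the f = 1 value is a bound that the Off Treatment assessment makes unrealistic as a typical result. These figures rest on equal, independent risk per infusion and on background rates from other prexasertib studies. The change is worth making because it is cheap, not because a material bias has been shown.

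**What to change.** - In 5.6 and in footnote k of Table 10, replace the reference to serious adverse events with all adverse events, serious or not, through 30 days after the last infusion. Use the visit or contact that footnote k already requires.
- Add that contact to the Adverse Events row of Table 10.
- Reconcile the 30-day clock. It runs from removal from protocol therapy in 5.6, from the last dose in 7.2, and from the end of study treatment in footnote k. These dates can differ, since 6.3 allows infusions to be held for up to 4 weeks before removal. State one starting date and use it throughout, so that the collection period for the toxicity analysis has a defined end.

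The cost is an amendment to wording, some extra case report form entries at a contact already made, and slightly less favourable reported toxicity rates. No new visit is needed.
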